## **6.4 Study Pause Rules**

The investigators, study medical monitor, and Sponsor will monitor for events that could trigger a study pause. Study pause rule criteria, events, and thresholds are described in [Table 5](#).

**Table 5: Pause Rule Criteria, Events, and Thresholds**

Pause Rule Criterion	Event	Participant Threshold for Triggering Study Pause
1	Any death due to SARS-CoV-2 infection	$\geq 1$
2	Any SAE or Grade 4 AE that cannot be reasonably attributed to a cause other than vaccination	$\geq 1$
3	ICU Admission due to COVID-19	$\geq 1$
4 	Individual Grade 3 or higher solicited local AR lasting $\geq 24$ hours and occurring within 7 days of injection (Days 1-7)	At least 2 participants and $\geq 5\%$ of the dosed participants in an age group
5 	Individual Grade 3 or higher solicited systemic AR lasting $\geq 24$ hours and occurring within 7 days of injection (Days 1-7)	At least 2 participants and $\geq 10\%$ of the enrolled participants in an age group
6 	Any $\geq$ Grade 3 or higher unsolicited AE that cannot be reasonably attributed to a cause other than vaccination	At least 2 participants and $\geq 5\%$ of the enrolled participants in an age group

Abbreviations: AE = adverse event; AR = adverse reaction; COVID-19 = coronavirus disease 2019; ICU = intensive care unit; SAE = serious adverse event; SARS-CoV-2 = severe acute respiratory syndrome coronavirus 2.

 “Individual AR” is defined as 1 AR type, eg, pain, erythema, or headache could each be an “individual AR.”

 Events in participants receiving booster doses will be considered separately from the events during the primary vaccination series.

If any of the thresholds for a study pause is met, the Sponsor will immediately suspend further enrollment and/or study dosing by notifying all investigators. Such a suspension will remain in force until the threshold events are reviewed by the DSMB and a recommendation to continue is provided to the Sponsor.

The investigator or designee is responsible for reporting to the Sponsor, via the electronic data capture (EDC) system, each event that potentially meets any pause rule criterion within 24 hours of observation. If an SAE assessed as related to IP by the investigator is reported at any point, the Sponsor’s medical monitor is responsible for a rapid assessment (with the Sponsor’s Medical and Safety team) of whether pause rule # 2 has been met; the Sponsor medical monitor may consult with the DSMB chair as an independent entity to make that determination, as described in the DSMB charter.

The Sponsor will inform the DSMB of any event that meets any pause rule criterion. The DSMB will review all available study data to help adjudicate such events in accordance with the DSMB charter.

The Sponsor will notify the Center for Biologics and Evaluation Research within 48 hours in the event of a study pause. In the event of a study pause, all safety and immunogenicity assessments will continue per protocol. The window allowance for injection visits may be extended by an additional 7 days (ie, + 21 days) for affected participants at the discretion of the Sponsor.

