## 3 STUDY DESIGN

### 3.1 General Design

This is a Phase 2/3, three-part, open-label, dose-escalation, age de-escalation and randomized, observer-blind, placebo-controlled expansion study intended to infer the effectiveness of mRNA-1273 in children aged 6 months to < 12 years. The study population will be divided into 3 age groups (6 years to < 12 years, 2 years to < 6 years, and 6 months to < 2 years), and up to 3 dose levels (25, 50, and 100 µg) of mRNA-1273 will be evaluated (and a third dose or an optional booster of 10 or 25 µg).

The study will be conducted in 3 parts. Part 1 of the study will be open-label and consist of dose-escalation and age de-escalation in approximately 1,275 participants to select the dose for each age group with the highest number enrolled in the oldest age group ([Table 3](#)). Part 2 of the study will be a placebo-controlled observer-blind evaluation of the selected dose in up to 12,000 participants (up to 4,000 participants each in the 6 years to < 12 years, 2 years to < 6 years, and the 6 months to < 2 years of age groups). Part 3 will be an open-label alternative dosing assessment in approximately 300 participants in the 6 year to < 12 year old age group to assess reactogenicity and immunogenicity of a lower dose regimen. No participants in Part 1 will participate in Part 2 or Part 3 of the study, and no participant in Part 2 will participate in Part 3 of the study.

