In order to expedite the study of the safety of mRNA-1273 in school-aged children 6 years to < 12 years of age; Part 1 will enroll a total of approximately 375 participants per dose (both at the 50 and 100 µg dose levels) in this age group (6 years to < 12 years). The first 75 of these participants per dose will be included in the safety evaluation for dose-escalation and age de-escalation as well as the immunogenicity assessment needed for dose selection, as applicable. Additionally, approximately 300 participants per dose will be enrolled to assess for any AE occurring at 1% or higher. The sample size for Part 2 in this age group (6 years to < 12 years) will be adjusted to approximately 1700 participants. Conversely, approximately 75 participants in the middle age group (2 years to < 6 years) will be enrolled per dose in Part 1 for safety and dose selection and Part 2 will utilize the dose selected in Part 1 to inform on AEs occurring at a frequency of 1% or greater. In the youngest age group (6 months to < 2 years), approximately 150 participants will be enrolled per dose in Part 1 for safety and dose selection and Part 2 will utilize the dose selected in Part 1 to inform on AEs occurring at a frequency of 1% or greater. For details, please refer to [Section 7.5](#).

The study will begin with the oldest age group (6 years to < 12 years) and age de-escalate as described under Study Progression. Each age group will begin with Part 1 and may advance to Part 2 and Part 3 independently. For details, please refer to the study schematic in [Figure 1](#).

The mRNA-1273 investigational vaccine or placebo will be administered as 2 IM injections approximately 28 days apart for Part 1 and Part 2. For Part 3, the mRNA-1273 investigational vaccine will be administered as 3 IM injections approximately 28 days apart for the 2 doses of primary series followed by a third dose at least 3 months and up to 5 months after receipt of the second dose of the primary series. The mRNA-1273 dose levels that will be evaluated in each age group in Part 1, Part 2 and Part 3 of the study are given in [Table 3](#).

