#### **Optional Booster Doses:**

Per Amendment 7, Part 1 (all ages) and 6 to < 12 year old Part 2 participants will be offered an optional booster dose of mRNA-1273 lower than the chosen primary series for each age group ([Table 4](#)), at least 6 months (Part 1 participants and Part 2 participants in Study Arm 8; Part 2 placebo recipients from Study Arm 9, who crossed over to mRNA-1273 after unblinding) after Dose 2 of mRNA-1273.

[figure not shown]
In Amendment 9, all participants in all age groups in Part 1 and Part 2 who have not yet received a booster dose will be offered a booster dose with mRNA-1273.214 (instead of mRNA-1273).

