### **Optional Booster Doses:**

All participants in Part 1 and Part 2 who choose to receive a booster dose will provide blood specimens for immunogenicity and serostatus on BD-Day 1 (prior to booster dose). Subgroups of participants who receive a booster dose will also provide one more blood specimen post-booster (see [Table 16](#) for details).

All participants in Part 3 of the study will provide blood specimens for immunogenicity on Day 1 (prior to the first dose) and will also provide additional samples at Day 57, Day 149/BD-Day 1 (prior to third dose), and one month after the third dose on Day 177/BD-Day 29. The first 150 participants (Sub-Cohort F) will also have a blood draw on Day 329/BD-Day 181; the second 150 participants (Sub-Cohort G) will also have a blood draw on Day 514/BD-Day 366.

Participants and their parent(s)/LAR(s) will be instructed on the day of the first dose (Day 1) and reminded on the day of the second dose (Day 29) and day of booster/third dose (BD-Day 1) how to document and report solicited local or systemic ARs in a provided electronic diary (eDiary). Solicited ARs, unsolicited AEs, MAAEs, AEs leading to withdrawal, AESIs, and SAEs will be assessed as described in [Section 7.1](#), according to the time points in in the SoAs ([Section 10.1](#)).

An unscheduled visit may be prompted by reactogenicity issues, or new or ongoing AEs, and while Part 2 of the trial is still blinded for any age group, illness visit criteria for COVID-19. Illness visit criteria for COVID-19 will be applicable while Part 2 of the trial is still blinded.

While Part 2 is still blinded for any age group, if a participant meets the pre-specified criteria of suspicion for COVID-19, the participant will be asked to return within 72 hours or as soon as possible to the study site for an unscheduled illness visit, to include a nasal swab sample (for RT-PCR testing to evaluate for the presence of SARS-CoV-2 infection) and other clinical evaluations. If a study site visit is not possible, a home visit may be arranged to collect the nasal swab sample and conduct clinical evaluations. The study site may collect an additional nasal swab sample for SARS-CoV-2 testing to be able to render appropriate medical care for the study participant as determined by local standards of care. Additionally, clinical information will be carefully collected to evaluate the severity of the clinical case.

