Abbreviations: AE = adverse event; AESI = adverse event of special interest; AR = adverse reaction; BD = booster (third) dose; BMI = body mass index; C = clinic visit; COVID-19 = coronavirus disease 2019; D = day; eCRF = electronic case report form; EDC = electronic data capture; eDiary = electronic diary; FDA = Food and Drug Administration; IP = investigational product; IRB = institutional review board; LAR = legally authorized representative; M = month; MAAE = medically attended adverse event; MIS-C = multisystem inflammatory syndrome in children; RT-PCR = reverse transcriptase polymerase chain reaction; SAE = serious adverse event; SARS-CoV-2 = severe acute respiratory syndrome coronavirus 2; SC = safety (telephone) call; SFU = safety follow-up; TMV = telemedicine visit.

**Note:** In accordance with FDA Guidance on Conduct of Clinical Trials of Medical Products during COVID-19 Public Health Emergency (FDA March 2020), investigators may convert study site visits to home visits or telemedicine visits (with the exception of Screening, Day 1, Day 29, and Day 149) with the approval of the Sponsor.

1. Screening Visit and Day 1 may be combined on the same day. Additionally, the Screening Visit may be performed over multiple visits if performed within the 28-day screening window.
2. If the visit for the second dose (Day 29) is disrupted and cannot be completed at Day 29 (+7 days) as a result of the COVID-19 pandemic (self-quarantine or disruption of study site activities following business continuity plans and/or local government mandates for “stay at home” or “shelter in place”), the visit window may be extended to Day 29 + 21 days. When the extended visit window is used, the remaining study visits should be

rescheduled to follow the intervisit interval from the actual date of the second dose. Refer to [Section 6.1.1](#) for individual participant criteria for delay of study vaccination.

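### Pause rules 5 and 6 (Table 5) keep an enrolled-in-age-group denominator when booster events are counted separately, so a separate count for a small dose group such as the Part 3 third dose has a trigger that is almost or wholly out of reach

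*Protocol*

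**What the plan says.** Table 5 in Section 6.4 lists six pause criteria. Rules 1 to 3 fire at one participant. Rules 4 to 6 need at least two participants and a percentage:

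- Rule 4 (Grade 3 or higher solicited local reaction): 5% "of the dosed participants in an age group".
- Rule 5 (Grade 3 or higher solicited systemic reaction): 10% "of the enrolled participants in an age group".
- Rule 6 (Grade 3 or higher unsolicited AE with no reasonable cause other than vaccination): 5%, with the same *enrolled* denominator as rule 5.

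Footnote 2 is attached to rules 4 to 6: "Events in participants receiving booster doses will be considered separately from the events during the primary vaccination series". It gives no denominator for the separate count.

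Part 3 is an "open-label alternative dosing assessment in approximately 300 participants" aged 6 to <12 years (Section 3.1), who receive three 25 µg doses. Section 3.1 gives two sizes for Part 2 in this age group: up to 4,000, and a statement that it "will be adjusted to approximately 1700 participants". If any threshold is met, the Sponsor must suspend enrolment and/or dosing at once until the DSMB has reviewed the events.

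**The concern.** A percentage rule needs a numerator and a denominator drawn from the same children. Footnote 2 narrows the numerator to booster recipients. Rules 5 and 6 still divide by everyone enrolled in the age group, most of whom never received the dose being counted. The more enrolment exceeds the dose group, the less the rule can do.

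The Part 3 third dose shows this most clearly. It goes to about 300 children in the largest age group, and solicited reactions are collected by eDiary after it (Section 3.1.1.2, Table 17). Rules 4 to 6 exist to catch a cluster of non-serious Grade 3 reactions, which rules 1 to 3 do not cover. Because rule 4 says *dosed* and rules 5 and 6 say *enrolled*, a programmer cannot simply treat the two words as the same.

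**Working it through.** **Inputs (age group 6 to <12 years).** Part 1: about 750 (synopsis, Number of Participants). Part 2: up to 4,000 (Sections 3.1 and 5.2), or about 1,700 (also Section 3.1). Part 3: about 300. Thresholds: 10% for rule 5 and 5% for rule 6 (Table 5).

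Table 5 prints no absolute counts to reproduce. The protocol's enrolment totals do reproduce: 750 + 225 + 300 = 1,275 in Part 1 and 3 × 4,000 = 12,000 in Part 2.

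**Formula.** Trigger = percentage × denominator, rounded up. Compare it with the 300 children who could contribute an event.

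| Denominator | Size | Rule 5 (10%) | Rule 6 (5%) |
|---|---|---|---|
| Enrolled, Part 2 = 1,700 | 750 + 1,700 + 300 = 2,750 | 275 of 300 (92%) | 137.5, so 138 of 300 (46%) |
| Enrolled, Part 2 = 4,000 | 750 + 4,000 + 300 = 5,050 | 505 of 300 (unreachable) | 252.5, so 253 of 300 (84%) |
| Third-dose recipients | 300 | 30 of 300 | 15 of 300 |

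Rule 5 is out of reach when 0.10 × (750 + 300 + N) > 300, that is, when Part 2 enrolment N exceeds 1,950. Rule 6 would need more than 6,000 enrolled to be out of reach, so it stays possible in principle.

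**Does *booster* in footnote 2 include the third dose?** Three places suggest that it does. Table 17, the Part 3 schedule, has the abbreviation "BD = booster (third) dose". Section 3.1 labels the third-dose visit as booster-dose Day 1. Section 3.1 also describes the last dose across Study Arms 1 to 14, which include Part 3, as Dose 2 or a booster dose. Against this, Section 3.1.1.2 and Table 10 name booster and third dose side by side where both are meant, and footnote 2 does not.

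**Cost of a recipient denominator.** Suppose the rule is checked after every child over 300 recipients and fires at the first point with at least two events and at least the stated percentage. The true rates below are assumptions.

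| Rule | Assumed true rate | Chance of at least 2 early on | Chance of ever firing over 300 |
|---|---|---|---|
| 5 | 2% | 6% (first 20) | 7% |
| 5 | 5% | 26% (first 20) | 34% |
| 4 or 6 | 1% | 6% (first 40) | 7% |
| 4 or 6 | 2% | 19% (first 40) | 24% |

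The early figures are binomial probabilities with n = 20 (where two events make 10%) and n = 40 (where two make 5%). For rules 4 and 5 the figures concern one reaction type. Footnote 1 counts each type separately and Table 8 lists seven systemic types, so the chance across types is higher.

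**The case against.** The strongest reply is that *separately* already implies a recipient denominator. On this view, once footnote 2 isolates booster recipients a safety team would naturally divide by them, and nobody would program a rule that cannot fire. That may be the intent, and on that reading the rules work. But rules 5 and 6 print a different denominator, and Table 5 does not say that the footnote changes it.

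A reader might infer that rule 5 simply cannot fire after the third dose, because 505 exceeds 300. The documents do not support that as a flat statement. It needs the third dose to be counted separately, Part 2 to reach 4,000 in this age group, and *enrolled* to be taken literally. At 1,700 the rule can be reached in principle, at 275 of 300. A reader might also infer that footnote 2 leaves the third dose out. Usage in Section 3.1 and Table 17 points the other way, so what remains is an unnamed dose rather than an exclusion.

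It would also be too strong to say that the denominator is what disables rule 5 after mRNA-1273.214. Section 7.4.3 states that no eDiary is used after that booster and that reactions are reported only if medically attended, serious or leading to discontinuation. Missing data limit rule 5 there, whatever the denominator. Rule 6 is different: Section 7.4.8 defines a severe AE as needing intensive therapeutic intervention. Such events would ordinarily be medically attended, and Table 19 collects those.

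Other protection is real. Rules 1 to 3 fire at one event, the DSMB reviews safety throughout (Section 7.5.2), and the third dose is at a level these children have already received twice. This limits the seriousness of the gap but does not supply the missing denominator. The DSMB charter is not shown; Section 6.4 cites it for the rule 2 determination and for adjudicating events, not for denominators.

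**Conclusion.** The point holds as a wording defect with a practical effect. Read as printed, rules 5 and 6 divide a separate booster or third-dose count mostly by children who did not receive that dose. The triggers for the third dose are then about 9 to 17 times those on a recipient denominator (275/30 and 138/15 at the smaller Part 2 size, 505/30 and 253/15 at the larger). These figures assume about 300 third-dose recipients, a separate count for that dose, and the literal *enrolled* denominator. For mRNA-1273.214 the point matters mainly for rule 6. It should be fixed, but as a modest safety correction: single-event rules and DSMB oversight are untouched, and the intended reading may already be the workable one.

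**What to change.** In rules 4 to 6, make the denominator *participants in the age group who have received that dose*. Apply it separately to the primary series and to each booster or third dose (mRNA-1273 booster, mRNA-1273.214 booster, Part 3 third dose). Name the Part 3 third dose in footnote 2. Keep the percentages and the two-participant floor. Do not use the booster/third-dose Safety Set of Table 10 as the denominator, because it pools the two.

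The drafting cost is a few words in Table 5 and a change to the pause-rule programming; dosing records already exist. The operating cost is more pauses on few events, at the probabilities given above, each going to DSMB review. The change does not restore solicited-reaction data after mRNA-1273.214.

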## **6.5 Lost to Follow-up**

A participant will be considered LTFU if he or she repeatedly fails to return for scheduled visits without stating an intention to withdraw consent/assent and is unable to be contacted by the study site. The following actions must be taken if a participant fails to return to the clinic for a required study visit:

- The study site staff must attempt to contact the participant and reschedule the missed visit as soon as possible, counsel the participant and his/her parent(s)/LAR(s) on the importance of maintaining the assigned visit schedule and ascertain whether the participant wishes to and/or should continue in the study.
- Before a participant is deemed LTFU, the investigator or designee must make every effort to regain contact with the participant (where possible, 3 telephone calls and, if necessary, a certified letter to the participant's last known mailing address or local equivalent methods). These contact attempts (eg, dates of telephone calls and registered letters) should be documented in the participant's medical record.
- A participant who continues to be unreachable or continues to be noncompliant with study visits or procedures will be considered to have withdrawn from the study.
- A participant should not be considered LTFU until due diligence has been completed.

## 7 STUDY ASSESSMENTS AND PROCEDURES

Before performing any study procedures, all potential participants and/or participants' parent(s)/LAR(s) will sign an ICF (as detailed in [Section 10.2.6](#)). Participants will undergo study procedures at the time points specified in the SoAs ([Section 10.1](#)). A participant can also be seen for an unscheduled visit at any time during the study. An unscheduled visit may be prompted by reactogenicity issues, illness visit criteria for COVID-19 (as applicable while Part 2 of study is still blinded for any age group), or new or ongoing AEs. The study site also has the discretion to make reminder telephone calls or send text messages to inform the participant and/or participant's parent(s)/LAR(s) about visits, review eDiary requirements, or follow-up on ongoing or outstanding issues.

In accordance with "FDA Guidance on Conduct of Clinical Trials of Medical Products during COVID-19 Public Health Emergency" ([DHHS 2020](#)), investigators may convert study site visits to home visits or telemedicine visits with the approval of the Sponsor. Such action should be taken to protect the safety and well-being of study participants and study site staff or to comply with state or municipal mandates.

General considerations for study assessments and procedures include the following:

- Protocol waivers or exemptions are not allowed. The study procedures and their timing must be followed as presented in in the SoAs ([Section 10.1](#)). Adherence to the study design requirements is essential and required for study conduct.
- Immediate safety concerns should be discussed with the Sponsor immediately upon occurrence or awareness to determine if the participant should continue study treatment or participation in the study.
- All screening evaluations must be completed and reviewed to confirm that potential participants meet all eligibility criteria. The investigator will maintain a screening log to record details of all participants screened and to confirm eligibility or record reasons for screening failure, as applicable.
- Procedures conducted as part of the participant's routine clinical management (eg, pregnancy test) and obtained before signing of the ICF may be utilized for screening or baseline assessments provided the procedures met the protocol-specified criteria and were performed within the time frame defined in in the SoAs ([Section 10.1](#)).

## 7.1 Safety Assessments and Procedures

Safety assessments will include monitoring and recording of the following for each participant, according to the SoAs ([Section 10.1](#)):

- Solicited local and systemic ARs ([Section 7.4.3](#)) that occur during the 7 days following each injection (ie, the day of injection and 6 subsequent days). Solicited ARs will be recorded daily using eDiary ([Section 7.1.1](#)).
- Unsolicited AEs observed or reported during the 28 days following each injection (ie, the day of injection and 27 subsequent days). Unsolicited AEs are defined in [Section 7.4.1](#).
- AEs leading to discontinuation from dosing and/or study participation from Day 1 through the last day of study participation.
- MAAEs ([Section 7.4.4](#)) from first dose on Day 1 through the entire study period.
- SAEs ([Section 7.4.2](#)) from first dose on Day 1 through the entire study period.
- AESIs ([Section 7.4.5](#)) including MIS-C and myocarditis and/or pericarditis, through the entire study period.
- Physical examination findings ([Section 7.1.4](#)).
- Assessments for SARS-CoV-2 infection from Day 1 through study completion ([Section 7.1.5](#)).
- Details of all pregnancies in female participants after the start of study treatment and until the end of their participation in the study ([Section 7.4.6](#)).

